A MRI-Controlled, multicenter, Baseline-to-Treatment, 32-weeks, open-label, Phase IIa Trial in Patients with Relapsing-Remitting Multiple Sclerosis or Clinically Isolated Syndrome
- Short Title:** SABA
- Study Phase:** IIa
- Study Design:** Phase IIa study consisting of a run-in phase, a dose finding phase, a stabilization phase, a continued treatment phase and a follow-up.

The trial will consist of:

- 12 week **run-in phase** (4 monthly baseline MRIs)
- **Stage 1: Dose finding:** Treatment with Boswellic acid will be initiated by escalating the dose to the maximum individually well tolerated dose within the first 4 weeks of treatment. Dose finding period of up to 4 weeks. Safety with respect to the effect of Boswellic acid (BA) on MS/CIS will be monitored by MRI and clinical assessment. The highest individual well tolerated dose will be used for each patient in Stage 2.
- **Stage 2: Stabilization:** A phase of 4 weeks will be used for adjustment of the dose to a continuously well tolerated dose. Patients not tolerating the dose established in Stage 1 will be treated with their maximum individually well tolerated dose.
- **Stage 3: Treatment:** A phase of 6 months will follow the dose finding and stabilization phases for a total of 8 months treatment. MRI will be used as the primary outcome measure to assess safety and to determine the effect of Boswellic acid on disease activity. The mechanism of action of Boswellic acids will be examined in parallel to the MRI and clinical assessment.
- **Stage 4: Follow-Up:** A phase of 4 months will follow the treatment phase. Patients are offered to continue study drug or to stop study drug after month 8. In either case the final follow-up visit will take place at month 12 including a complete clinical and MRI assessment.

Study rationale: Boswellic acids (BA) are the main components of extracts from the resin of the frankincense tree (*Boswellia serrata*).

These BAs have known anti-inflammatory activities and have been used literally for thousands of years in traditional Eastern and Asian medicine. Recently, the molecular mechanism of action of several specific BAs has been defined as inhibition of cathepsin G, microsomal prostaglandin synthase (mPEGS)-1, and 5-lipoxygenase (5-LO), i.e. factors that are involved in cell migration, inflammation and neurodegeneration in Multiple Sclerosis.

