The individual well tolerated dose from Stage 1 will be used for each patient in a subsequent 4-week stabilization phase during which the dose will be observed for continuous safety and toleration. Afterwards this individual maximal well tolerated dose will be used in Stage 3 of the study for further 6 months. Patients not tolerating the minimum dose of 800mg t.i.d. will be excluded from the study.

Stage 3

In Stage 3 of the study, patients will be treated with their individual well tolerated dose of BOSWELAN as assessed in Stage 2 subsequently for six months. The minimum dose for patients to be considered evaluable in the primary statistical analysis will be 800mg t.i.d..

The primary outcome will assess the change in mean Gd-enhancing lesion number from the baseline to that observed over months 5, 6, 7 and 8 since a delay in treatment effect is expected. In addition to MRI evaluation, patients will have monthly neurological evaluations and immunological assessment.

Stage 4

After completing Stage 3 patients are offered to continue their BOSWELAN dose for 4 months or to stop drug intake after month 8. In any case patients are seen for clinical and MRI-follow-up at month 12 at the study center.

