7.3.1 Subject Withdrawal from the Study

A subject *must* permanently discontinue study drug treatment and *must* be withdrawn from the study prematurely for any of the following reasons:

The subject becomes pregnant. Treatment must be *immediately* discontinued. The pregnancy must be reported to the study center (study coordinator/treating physician/PI) immediately. Information about the subject, the subject's pregnancy, the outcome of the pregnancy, and the status of the infant at 8 to 12 weeks of age will also be collected.

The subject desires to discontinue study drug treatment under this protocol. Patients have the right to withdraw from the study at any time and for any reason. The investigator also has the right to withdraw patients from the study in the event of an intercurrent illness, non-compliance after a prescribed procedure, protocol violations, administrative reasons, other reasons.

The subject receives or wishes to start any restricted medication listed in table 2 except corticosteroids.

At the discretion of the investigator for medical reasons or for non-compliance.

The study will be prematurely terminated for an individual if an exclusion criteria occurs during the study.

Dosing in stage 1 has to be discontinued in case of a SAE. If dosing is stopped for greater than 2 weeks, the study medication will be stopped in that patient and the patient will be withdrawn prematurely from the study.

The reasons for discontinuation of the study drug must be recorded in the subject's Clinical Center patient file and the respective case report forms (CRFs).

Patients discontinuing dosing will be followed for an additional 2 months. If discontinuation was because of a serious adverse event, the patient will be followed until the event is resolved or stabilized, but not shorter than 2 months.

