- Recording of concomitant medication.
- Cranial MRI.

Month 7 (\pm 7 days)

- Monitoring of adverse events.
- Vital signs and body weight.
- Haematology: see 11.3..
- Blood chemistries: see 11.3..
- Urinalysis: see 11.3..
- Urine pregnancy test for women of child-bearing potential.
- EDSS, SNRS, MSFC.
- Recording of concomitant medication.
- Cranial MRI.

Month 8 (\pm 7 days)

- Monitoring of adverse events.
- A complete physical examination.
- Vital signs and body weight.
- Haematology: see 11.3..

- Blood chemistries: see 11.3..
- Urinalysis: see 11.3..
- Urine pregnancy test for women of child-bearing potential.
- Immunological measures.
- Biomarker Assessment.
- EDSS, SNRS, MSFC,
- HAQUAMS, MSIS29, UNDS.
- Recording of concomitant medication.
- Cranial MRI.

* Optional for patients choosing to continue treatment with BOSWELAN:

- **Month 9 (\pm 7 days) ***
 - Monitoring of adverse events (Telephone call)
 - EDSS (Telephone call)
- **Month 10 (\pm 7 days) ***
 - Monitoring of adverse events (Telephone call).
 - EDSS (Telephone call)
- **Month 11 (\pm 7 days) ***
 - Monitoring of adverse events (Telephone call).
 - EDSS (Telephone call)

Extension: Month 12 (\pm 7 days) / Early Termination

- Monitoring of adverse events.
- A complete physical examination.
- Vital signs and body weight.
- Haematology: see 11.3..
- Blood chemistries: see 11.3..
- Urinalysis: see 11.3..
- Urine pregnancy test for women of child-bearing potential.
- Immunological measures.
- Biomarker Assessment.
- EDSS, SNRS, MSFC.
- HAQUAMS, MSIS29, HADS, Fatigue Severity Scale
- Recording of concomitant medication.
- Cranial MRI.

Unscheduled Visits / Relapse

In case of Relapse mandatory

- Monitoring of adverse events.

- Vital signs and body weight
- Recording of concomitant medication.
- Cranial MRI
- EDSS, SNRS, MSFC.
- HAQUAMS, MSIS29, HADS, Fatigue Severity Scale
- HARAS
- Other procedures as indicated by the investigator

Relapse follow-up

- Monitoring of adverse events.
- Vital signs and body weight
- Recording of concomitant medication.
- EDSS, SNRS, MSFC.
- HAQUAMS, MSIS29, HADS, Fatigue Severity Scale
- HARAS
- Other procedures as indicated by the investigator

All other unscheduled visits including unscheduled drug dispensation

- Monitoring of adverse events.
- Recording of concomitant medication.
- Other procedures as indicated by the investigator

11. Safety Assessments

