13.3.3 Clinical Safety Measures

The clinical measures are the changes in EDSS, SNRS, MSFC, and relapse rate. EDSS score will be obtained monthly as long as patients are treated with BOSWELAN either clinically or by telephone according to (62). The analyses will follow the same sequence of analyses as described for MRI. Comparison will always be made between baseline (week 0) and month 8 or earlier if treatment is stopped early.

14. Evaluation of Efficacy

Three efficacy populations will be analyzed for the primary outcome measures total Gd enhancing lesions and lesion volume:

The primary outcome in Stage 2 will first compare lesion (Gd-contrasting lesions) frequency (mean number of lesions) and area occurring during the 4 month baseline to lesion frequency and area occurring during months 5, 6, 7, 8 on treatment in patients treated with a dose of at least 800 mg t.i.d.

A secondary analysis will compare lesion frequency occurring over the 4 months of baseline to that occurring during over all treatment months.

An intention-to-treat analysis will be performed with all patients, all time on study.

Wilcoxon signed-rank test will be used for analysis of the primary endpoints.

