1. Patients early in the course of MS who have not elected to receive approved therapy will have the indications for approved therapy and the benefits of that therapy discussed with the patient by the referring physician or by a physician at the MS outpatient unit at the UKE, Hamburg or the Charité Berlin not directly involved in the current study. This discussion will occur prior to discussion of the trial of BOSWELAN. Documentation of the patient's election to defer approved therapy will be documented in the medical record. Further, the informed consent will review the benefits of the approved therapies and the potential risk of deferring this therapy.
2. The patient together with the patient's treating physician outside the MS outpatient unit at the UKE (inims), Hamburg or the Charité, Berlin will make the determination that a patient has failed approved therapy. In general, treatment failure means that the patient has continued to have relapses at a rate similar to the frequency prior to treatment, that the patient is showing progression of disability or that the patients cannot tolerate the treatments. The reason for considering the patient a treatment failure will be documented in the medical record.

After discontinuation of treatment patients will be monitored for an additional four months (months 9-12) and be offered counselling regarding further treatment.

17. Optional Substudy on pharmacokinetic effects

To gain further insight into the dose-dependent pharmacokinetics of BOSWELAN and to see if there is a linear relationship between dose and plasma level, an optional pharmacokinetics substudy will be offered to a minimal of 5 and maximally 10 patients participating in the above mentioned study. These five to ten patients will be asked to donate blood samples during stage 2 of the study (dose titration) on the following days and at the described timepoints:

Days	Dosing schedule	Blood samples taken
Day 0	1-0-0	- pre-dose - 1/2 hrs. after intake - 1 hrs. after intake - 2 hrs. after intake - 3 hrs. after intake

		- 5 hrs. after intake - 8 hrs. after intake - 24 hrs. after intake
Day 9:	2-2-2	- pre-dose - 1 hrs. after intake - 2 hrs. after intake - 3 hrs. after intake
Day 18	3-3-3	- pre-dose - 1 hrs. after intake - 2 hrs. after intake - 3 hrs. after intake
Day 28	4-4-4	- pre-dose - 1 hrs. after intake - 2 hrs. after intake - 3 hrs. after intake

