Appendix A: Study Flow Sheet

	SCREENING				STAGE 1 DOSE TITRATION									STAGE 2 STABILIZATION	STAGE 3 TREATMENT					STAGE 4 FOLLOW-UP					
	Month -3 (Screening)	Month -2 (+7 days)	Month -1 (+7 days)	Day 0 (+7 days)	Day 1 (±1 days)	Day 4 (±1 days)	Day 7	Day 10	Day 13 (±1 days)	Day 15	Day 18	Day 22	Day 25	Day 28	Month 2 (+7 days)	Month 4 (+7 days)	Month 5 (+7 days)	Month 6 (+7 days)	Month 7 (+7 days)	Month 8 (+7 days)	Month 9** (+7 days)	Month 10** (+7 days)	Month 11**	Month 12 (+7 days)	Month 12 /Early termination (+7 days)
Medical history	•																								
MS history	•																								
Physical examination	•			•										•	•			•		•					•
AE documentation		•	•	•										•	•		•	•	•	•					•
Inclusion/Exclusion criteria	•			•																					
Vital signs	•	•	•	•										•	•		•	•	•	•					•
Body weight	•	•	•	•										•	•		•	•	•	•					•
Blood chemistries	•			•										•	•		•	•	•	•					•
Haematology	•			•										•	•		•	•	•	•					•
Urinalysis	•			•										•	•		•	•	•	•					•
Hepatitis status	•																								
Immunology		•		•										•						•					•
Biomarker Assessment				•										•						•					•
Pregnancy test	•	•	•	•										•	•		•	•	•	•					•
First study drug dose				•																					
Telephone Call (AEs)					•	•			•						•						•	•	•		
Dose escalation					•	•	•	•	•	•	•	•													
Clinic observation				•																					
EDSS (* by telephone)	•	•	•	•										•	•	•*	•	•	•	•	•*	•*	•*		•
SNRS	•	•	•	•										•			•	•	•	•					•
MSFC	•		•	•										•			•	•	•	•					•
MRI	•	•	•	•										•	•		•	•	•	•					•
Concomitant medication	•	•	•	•										•	•		•	•	•	•					•
HAQUAMS, MSIS29, HADS, FSS	•			•										•			•	•		•					•
HARAS	At Month -3 for each Relapse within the last 12 Months and afterwards in case of Relapse/ Relapse follow-up																								

** for patients deciding to continue on study medication after month 8

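### Patients who stop BOSWELAN at month 8 have no scheduled contact until month 12, while continuers are called monthly, so Stage 4 adverse event and EDSS data are collected unequally and the schedule does not match Section 16.2

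*Protocol*

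**What the plan says.** Stage 4 begins with the patient's own choice to continue or stop the drug after month 8 (Protocol Sections 1 and 2.3). Section 4 describes the stopping path as a washout.

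- **Months 9, 10 and 11.** Section 10.1 lists two items for each month: "Monitoring of adverse events (Telephone call") and a telephone EDSS. The group of visits is headed "Optional for patients choosing to continue treatment with BOSWELAN". The Appendix A footnote for the same months reads "for patients deciding to continue on study medication after month 8".
- **Monthly EDSS.** Section 13.3.3 ties it to exposure: "EDSS score will be obtained monthly as long as patients are treated with BOSWELAN either clinically or by telephone".
- **Month 12.** This visit is for everyone. Section 2.3: "In any case patients are seen for clinical and MRI-follow-up at month 12 at the study center". Section 1 agrees: "In either case the final follow-up visit will take place at month 12 including a complete clinical and MRI assessment". Section 10.1 adds adverse events, laboratory tests, EDSS, SNRS and MSFC.
- **After stopping.** Section 16.2: "After discontinuation of treatment patients will be monitored for an additional four months (months 9-12"). Section 7.3.1, on withdrawal from the study: "Patients discontinuing dosing will be followed for an additional 2 months".
- **General duties.** Section 11.1 has adverse events collected for the whole study. Section 12.2 has each one followed until it resolves or the patient is stable, whether or not the drug continues. Section 10.1 makes an assessment with MRI and EDSS mandatory at relapse, with no condition about being on drug.

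**The concern.** Safety and tolerability are the primary objective (Section 3.1), and the safety parameters in Section 1 are headed as covering Stages 1 to 4, follow-up included. For patients who complete treatment, months 9-12 are the only planned time off drug. A site that follows Section 10.1 as written telephones the continuers each month and does not telephone the stoppers.

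Two things are then at stake. First, an adverse event or a passing neurological change in a stopper during months 9-11 reaches the record only if the patient reports it or remembers it at month 12. Second, if Stage 4 safety is tabulated by path, a difference between the paths would mix three things: the effect of the drug or of stopping it, the reasons patients chose their path, and the number of times they were asked. The third is created by the schedule and can be avoided. It would tend to give fewer recorded events off drug.

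Sites also face a practical conflict. Section 16.2 tells them that patients are monitored in months 9-12 after discontinuation, and the visit schedule gives them nothing to do in months 9-11.

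**Working it through.** The plan gives no figure on this point to reproduce. The check counts scheduled contacts and intervals.

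**Inputs**
- Contacts at months 9, 10 and 11, continuers only (Section 10.1, Appendix A).
- Contact at month 12, all patients (Sections 1, 2.3 and 10.1).
- Window of ±7 days on months 8 to 12 (Section 10.1).
- Month length of 28 days. This is an assumption for Stage 4, but it fits the title and Section 1, where 32 weeks correspond to 8 months of treatment: 32 / 8 = 4 weeks.

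**Scheduled assessments after month 8, up to and including month 12**

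| | Continue | Stop |
|---|---|---|
| Contacts | 3 + 1 = 4 | 0 + 1 = 1 |
| Adverse event enquiries | 4 | 1 |
| EDSS ratings | 4 | 1 |
| Laboratory tests | 1 | 1 |
| MRI | 1 | 1 |

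The imbalance is confined to adverse events and EDSS. Laboratory tests and MRI are the same on both paths.

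**Interval between scheduled contacts**
- Nominal: continuers 1 × 4 = 4 weeks; stoppers 4 × 4 = 16 weeks.
- Longest allowed, with one contact 7 days early and the next 7 days late: nominal days + 7 + 7.
  - Continuers: 28 + 14 = 42 days.
  - Stoppers: (4 × 28) + 14 = 112 + 14 = 126 days.

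**Against the DSMB cycle.** Section 12.1 has adverse events reported to the DSMB every 3 months. The stoppers' nominal gap is 4 months, so a reporting interval can pass in which no stopper has been asked about adverse events since stopping.

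**Sections side by side**
- 10.1, Appendix A and 13.3.3 agree with one another: monthly enquiry goes with taking the drug.
- 16.2 attaches monitoring in months 9-12 to having stopped. Its month numbers fit a planned stop at month 8.
- 7.3.1 gives 2 months. For a month 8 stopper that period would end at month 10, inside the gap. The sentence stands in the section on premature withdrawal, so it may not be meant for this patient.

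**Reach of the effect.** The primary MRI comparison uses the baseline scans and months 5-8 (Section 3.2). The clinical safety comparison runs from week 0 to month 8, or to an earlier stop (Section 13.3.3). Neither uses data from months 9-12.

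**The case against.** The best case for the plan has four parts.

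1. **Safety after stopping is observed.** A reader might infer from the empty months that it is not. The documents do not support that. Everyone has the full month 12 visit, a relapse triggers a mandatory assessment on or off drug, patients hold a site telephone number for reporting events (Section 12.1), and known events are followed to resolution. This stands. What is missing is active enquiry. The duty to follow known events does not make anyone ask about unknown ones. An EDSS change that has resolved by month 12 can still be caught, but only if it prompts a relapse visit.

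2. **The asymmetry looks intended.** Three sections agree on it, and closer contact during continued exposure is a recognisable choice. This stands as an explanation. It does not remove the tension with Section 16.2. That section names no contact frequency and could be read as meaning the month 12 visit plus the general duties, but then its wording needs to say so.

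3. **No stop-versus-continue comparison is planned.** A reader might infer that a main result is biased. It is not, since both main comparisons end at month 8. The point concerns the Stage 4 data themselves and any later description of them by path.

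4. **Sections 7.3.1 and 16.2 may describe different patients.** A reader might take 2 months against 4 months as a flat contradiction. Section 7.3.1 deals with permanent discontinuation and premature withdrawal, so the two periods can coexist. What stands is that the scope of the 2 months is not stated.

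The word optional in Section 10.1 could also mean that the calls are optional for continuers. Section 13.3.3 and Appendix A point to planned calls. If they were optional, 4 would be the maximum for continuers and the collection less uniform still.

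**Conclusion.** The point holds as an avoidable weakness in Stage 4 data collection, together with an inconsistency between the schedule and Section 16.2. The counts come directly from the visit schedule; the figures in days rest on 28-day months. How many events would be missed cannot be estimated, because the documents give no recall or reporting rates, and the conclusion does not need such a figure.

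It is worth correcting because safety is the primary objective and the correction is cheap. It does not threaten the primary MRI result or the planned clinical safety comparison.

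**What to change.** - Reconcile Sections 10.1 and 13.3.3 and Appendix A with Section 16.2, so that they describe the same follow-up for a patient who stops at month 8.
- Collect adverse events and telephone EDSS at months 9, 10 and 11 on one schedule for every patient who completes month 8, whichever path is chosen. In practice this means removing the restriction in the Section 10.1 heading and the Appendix A footnote, and extending the Section 13.3.3 sentence to Stage 4. The word optional would go with it.
- State in Section 7.3.1 whether the 2-month follow-up applies only to premature discontinuation.
- Report Stage 4 safety by chosen path, labelled as self-selected.

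This changes data collection only; dosing and treatment are untouched. Scheduled contacts become 4 on both paths, and the longest interval for stoppers falls from 126 to 42 days under the same 28-day assumption. The cost is three calls per stopper, using a procedure already in the protocol, and a short amendment.

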11.1 Clinical Safety Assessments

Clinical safety will be assessed by neurological examination including standardized rating scales for multiple sclerosis (EDSS (59), SNRS (60), MSFC (61)), relapse rate, general physical examination, and measurement of vital signs (temperature, heart rate, and blood pressure). Adverse events will be collected throughout the study.

11.2 MRI Safety Assessment

see section 7.3.2

11.3 Laboratory safety assessments

The specific laboratory parameters to be evaluated in this study are as follows:

- Blood chemistry: sodium, potassium, chloride, calcium, phosphate, creatinine, uric acid, urea, total bilirubin, GGT, ALT/GPT, AST/GOT, alkaline phosphatase, glucose, total protein, and albumin, lactate dehydrogenase, Fibrinogen, CRP, CK.
- Haematology: complete blood count with differential and platelet count, and coagulation studies (PT and PTT).

- Urinalysis: specific gravity, pH, protein, glucose, blood, Ketone, Nitrite, leucocytes and including a pregnancy test for women of child-bearing potential.
- Hepatitis Serology: will either be tested at screening or in case the patient has already been tested for Hepatitis during the last 12 months, these test results will be accepted.

12 Adverse Events

12.1 Adverse Events: Definition and management

The terms “relationship”, “serious” and “severity” used in this section, are defined in Table 3.

For the purposes of this study, adverse events are defined as any signs (including the clinical manifestations of abnormal laboratory results) or medical diagnoses noted by medical personnel, or symptoms reported by the patient, regardless of relationship to study drug, that:

- a) Have onset anytime after the first visit.

OR

- b) Have worsened since the event was previously reported (this includes worsening of signs, symptoms, or diagnoses that were present prior to dosing).

All adverse events reported by the patient or observed by study site personnel from the first visit until completion of a patient’s participation in the study must be recorded in the patient's file and CRFs. Serious Adverse events are to be recorded regardless of relationship to the study protocol and reported to the Sponsor.

The information to be recorded in the patient file will include, but not be limited to, relationship of the event to study drug and severity of the event. Specific instructions for recording adverse events will be provided under separate cover and will be reviewed by the study site personnel.

Patients will be given the name and phone number of personnel at the study site that can be called in the event of an emergency or to report an adverse event that is of concern to the patient. The contact information will also be displayed in the patient consent form.

Any serious adverse event (SAE, for definition see table 3) occurring during any time of the study (baseline and treatment phase) will be reported by the investigator to the Sponsor (here his deputy: the PI) immediately, but no longer than 24 hours after it becomes known.

The Sponsor will document all Severe Adverse Events (SAEs) reported by the Investigator.

The Sponsor will report all SAEs and all adverse events to the DSMB every 3 months.

The Sponsor will report all Suspected Unexpected Serious Adverse Reactions (SUSARs) to the relevant Ethics Committees and the relevant Competent Authorities at the latest 15 days after it becomes known. He will also inform all Investigators involved in the trial and the DSMB.

In case of a fatal or life threatening SUSAR the Sponsor will report all information relevant for judging the event immediately, at the latest 7 days after the event becomes known to the relevant Ethics Committees and the relevant Competent Authorities, as well as to all Investigators involved in the trial and the DSMB.

The Sponsor will further report immediately, at the latest 15 days after it becomes known, all circumstances that require a revision of the risk-benefit analysis of the investigational product to the above mentioned authorities. This especially includes:

- Singular cases of expected severe adverse events with an unexpected outcome
- Increased incidence of expected severe adverse events that are judged as being clinically relevant
- SUSARs which occur after termination of the clinical trial (max. 2 weeks after termination or exclusion)
- Events related to study procedures or development of the study medication, which could affect a subject's safety

The Sponsor will once a year submit the annual safety report to the Competent Authority(ies).

All person-related data will always be transmitted pseudonymised. Before reporting a SUSAR the subject will be unblinded.

Exception rules for the reporting:

In this clinical trial the following Serious Adverse Events are excluded from reporting:

- Severe or unexpected events which occur after screening or enrolment, but before first application of the investigational drug
- Hospital admissions for the purpose of diagnostic or therapeutic purposes which were planned before study inclusion
- Expected serious events, which could occur because of the administration of the investigational product and represent known effects of the investigational product.
- Hospital admissions for the purpose of treating a relapse

Table 3. Adverse Event Definitions

Serious Adverse Event	
Serious adverse events are defined as the following:	

 ▪ Any death. ▪ Any life-threatening* event, i.e., an event that places the subject, in the view of the investigator, at immediate risk of death from the event as it occurred (does not include an event that, had it occurred in a more severe form, might have caused death). ▪ Any event that requires or prolongs in-patient hospitalization. ▪ Any event that results in persistent or significant disability/invalidity. ▪ Any congenital anomaly/birth defect diagnosed in a child of a subject who participated in this study and received study drug. 	
* The term "life-threatening" refers to an event in which the subject was at risk of death at the time of the event; it does not refer to an event, which hypothetically might have caused death if it were more severe.	
Important medical events that may not be immediately life-threatening or result in death, disability or hospitalization but may jeopardize the patient or may require intervention to prevent one of the other outcomes listed in the definition above should also usually be considered serious.	
Relationship of Adverse Event to Study Drug	
Not related	Any reaction that does not follow a reasonable temporal sequence from administration of study drug AND that is likely to have been produced by the subject's clinical state or other modes of therapy administered to the subject.
Unlikely	Any reaction that does not follow a reasonable temporal sequence from administration of study drug OR that is likely to have been produced by the subject's clinical state or other modes of therapy administered to the subject.
Likely	A reaction that follows a reasonable temporal sequence from administration of study drug OR that follows a known response pattern to the suspected drug AND that could not be reasonably explained by the known characteristics of the subject's clinical state or other modes of therapy administered to the subject.
Definite	A reaction that follows a reasonable temporal sequence from administration of study drug AND that follows a known response pattern to the suspected drug AND that recurs with re-challenge, and/or is improved by stopping the drug or reducing the dose.
Severity of Adverse Event	
Mild	Symptom(s) barely noticeable to subject or does not make subject uncomfortable; does not influence performance or functioning; prescription drug not ordinarily needed for relief of symptom(s) but may be given because of personality of subject.
Moderate	Symptom(s) of a sufficient severity to make subject uncomfortable; performance of daily activity is influenced; subject is able to continue in study; treatment for symptom(s) may be needed.
Severe	Symptom(s) cause severe discomfort; symptoms cause incapacitation or significant impact on subject's daily life; severity may cause cessation of treatment with study drug; treatment for symptom(s) may be given and/or subject hospitalized.

